## I. Introduction

Preeclampsia is a life-threatening hypertensive disorder involving the heart and vasculature affecting 5-8% of pregnancies. Untreated, 2-10% of women develop eclampsia, defined as new onset of seizures in the setting of preeclampsia. Eclamptic seizures are estimated to occur in 2-8 per 10.000 deliveries in high-income countries (HIC) and with a higher prevalence of up to 16-69 per 10.000 deliveries in low-income countries (LIC). Eclampsia is associated with significant maternal and neonatal morbidity, with a case fatality rate as high as 25-50 % in LIC, and associated with a 16-26 fold odds of death in HIC. Associated maternal complications include intracranial hemorrhage (ICH), cerebral edema, acute kidney injury, acute respiratory syndrome (ARDS), cardiac failure, coagulopathy and postpartum hemorrhage. Obstetric and medical management include seizure prophylaxis and control, aggressive blood pressure management and the urgent delivery of the baby. Anesthesia management can be challenging and has to be tailored to the clinical condition of the eclamptic woman. Unless the usual contraindications to regional anesthesia (RA) apply, spinal anesthesia (SPA) has been described as the method of choice in parturients in whom the Glasgow Coma Scale (GCS) is  $\geq 14$ , and cardiac failure is absent. For patients with persistent decreased level of consciousness, general anesthesia (GA) is recommended. However, in eclamptic women both anesthesia techniques may be associated with significant complications. Raised intracranial pressure (ICP) present in eclamptic women raises the possibility of cerebellar tonsillar herniation in association with SPA. Cardiac diastolic dysfunction, with or without preserved ejection fraction, has been described in preeclamptic women. With preserved ejection fraction, induction of RA or GA is generally hemodynamically well tolerated. However, in women with decreased systolic function, induction of anesthesia can lead to life-threatening cardiovascular collapse, which may only be prevented by cautious titration of anesthesia agents. This might be in conflict with the need to administer high dosages of induction agents to blunt the hypertensive response to tracheal intubation that, if untreated, may lead to life-threatening ICH and pulmonary edema. Consequently, early detection of increased ICP and knowledge of cardiopulmonary function in the individual case are essential to the obstetric anesthetist to guide appropriate management.

Cardiopulmonary and optic nerve sheath point-of-care ultrasound (POCUS) protocols might be particularly suitable for this purpose. These involve a defined bedside ultrasound examination to identify critical cardiopulmonary pathophysiology, which may remain undetected by clinical examination alone. The identification of increased optic nerve sheath diameter (ONSD) on ultrasound may suggest raised ICP.

It is further well documented that the serum brain natriuretic peptide (BNP) level, a marker of cardiac dysfunction, is increased in preeclampsia. However, no data is available to confirm that elevated BNP levels identify those eclamptic women at risk for cardiopulmonary abnormalities.

Therefore, this study is planned to describe the prevalence and severity of cardiac, lung and ONS US abnormalities in women with eclampsia. In a recent study on POCUS findings in late onset preeclampsia, the absence of pulmonary interstitial syndrome (PIS) may exclude raised LVEDP. The **primary aim** of the current study is to examine the association between PIS, as identified by lung ultrasound, and cardiac dysfunction on echocardiography, in eclamptic women. The **secondary aims** are the performance of a comprehensive cardiac ultrasound assessment including a strain analysis, and to explore the association between PIS and ONSD, serum BNP and albumin.

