#### *F) Statistical analysis*

Data will be presented as mean and standard deviation for continuous variables, and frequency and percentage for categorical variables. For the a priori defined ultrasound outcomes of PIS, diastolic dysfunction, and increased ONSD, the prevalence and 95% confidence intervals will be calculated. In addition, the prevalence and 95% confidence intervals of systolic dysfunction and of raised LVEDP will be calculated.

Patients with and without ultrasound abnormalities will be compared with respect to admission systolic and diastolic blood pressures, clinical features of disease severity, and mean BNP levels using 2-sample t-test and the Chi-square test, for continuous and categorical variables respectively. The associations between PIS, increased ONSD or diastolic dysfunction with clinical severity features (=high arterial blood pressures, presence of pulmonary edema, headaches or visual disturbances, raised liver or renal laboratory parameters tests, and low platelet count), serum albumin level, BNP level, and between cardiac and pulmonary ultrasound abnormalities, will be explored using the 2-sample t-test and the Chi-square test, for categorical and continuous variables respectively. To adjust for multiple comparisons, including primary and secondary outcomes, a Benjamini-Hochberg correction will be applied using a 10% false discovery rate. Assuming that the p-value will result from 32 direct comparisons made in the study, the significance level will be adjusted to  $p < 0.025$ .

In order to determine pre- and post-test probabilities of PIS to predict elevated LVEDP, and of BNP at a level above 200 pg/ml to predict systolic dysfunction, diastolic dysfunction, elevated LVEDP, and the presence of PIS, sensitivity, specificity, positive and negative predictive value will be calculated.

Intra- and inter-observer agreement will be evaluated using the Bland and Altman method, after reviewing 10% of lung- (using total B-line score), cardiac- (using left ventricular internal diameter in diastole (LVEDD), and optic nerve (using the left optic nerve sheath

diameter) parameters; results will be expressed both graphically and quantitatively as mean difference (bias) and 95% limits of agreement.

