#### *Sample size calculation*

The sample size calculation is based upon the primary aim, which is to examine the association between PIS on lung ultrasound and raised LVEDP on cardiac ultrasound. Available data on women with late onset preeclampsia and severe features suggest that the incidences of PIS and raised LVEDP are 23/95 (24%; 95% CI: 16-34%), and 20/80 (25%; 95% CI: 16-36%) respectively. In that population, the proportion of women with raised LVEDP was 12% in patients without PIS, and 55% in those who had PIS. A sample size of 60 (45 LVEDP negative and 15 LVEDP positive) will be required to detect a significant difference in incidence of PIS between the 2 groups (52% [expected PIS positive rate in women with raised LVEDP] versus 15% [expected PIS positive rate in women with normal LVEDP]) with a power of 80% and significance level of 0.05. To allow for the possibility of poor image acquisition during positive pressure ventilation, 70 patients will be recruited.

[figure not shown]

Figure 1: Comparison of normal lung in Panel A versus B-line pattern in Panel B.

[figure not shown]

Figure 2 (Image from Ref.): Measurement of the optic nerve sheath diameter in the coronal axis. The view is obtained in a sharply demarcated circle, measured in its widest diameter (A). If edema is seen, the measurement is taken at the outer edge (B, outer calipers).

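### The primary comparison is sized at a significance level of 0.05 but analysed under a correction stated as p < 0.025, at which 60 women give about 72% power instead of 80%

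*Combined protocol and SAP*

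**What the plan says.** The primary aim is worded at two levels of detail. The Introduction says the aim is "to examine the association between PIS, as identified by lung ultrasound, and cardiac dysfunction on echocardiography, in eclamptic women", without saying which dysfunction. The Sample size calculation, a sub-item of F) Statistical analysis in the contents list, refers to "the primary aim, which is to examine the association between PIS on lung ultrasound and raised LVEDP on cardiac ultrasound". It plans for 60 women, 15 with raised and 45 with normal LVEDP, with PIS expected in 52% and 15% respectively, "with a power of 80% and significance level of 0.05". Recruitment is set at 70 to allow for poor images.

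The main text of F) Statistical analysis treats the cardiac findings as separate outcomes. Diastolic dysfunction is in the first list ("For the a priori defined ultrasound outcomes of PIS, diastolic dysfunction, and increased ONSD"), and the next sentence adds two more: "In addition, the prevalence and 95% confidence intervals of systolic dysfunction and of raised LVEDP will be calculated". Associations "between cardiac and pulmonary ultrasound abnormalities, will be explored using the 2-sample t-test and the Chi-square test". The same section then applies a Benjamini-Hochberg correction at a 10% false discovery rate. It states that this correction covers primary as well as secondary outcomes and, on a count of 32 comparisons, gives the resulting significance level as p < 0.025.

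**The concern.** A power statement holds only for the significance level at which the test will be run. Here the sizing uses 0.05, while the analysis text includes the primary outcome in a correction with a stricter stated level. Nothing in the plan reserves 0.05 for the primary test. Read literally, the primary comparison would be judged at p < 0.025 with a sample chosen for 0.05, so the chance of missing the planned difference would be larger than the 20% the plan implies.

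The wording of the aim adds a smaller difficulty. Systolic dysfunction, diastolic dysfunction and raised LVEDP all fit the Introduction's phrase, but planning rates and a power statement exist for raised LVEDP only.

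**Working it through.** **Inputs.** From the Sample size calculation: p1 = 0.52 (PIS with raised LVEDP), p2 = 0.15 (PIS with normal LVEDP), n1 = 15, n2 = 45, power 80%, level 0.05, 70 recruited. From F) Statistical analysis: 10% false discovery rate, 32 comparisons, p < 0.025. The plan does not say whether the level is one- or two-sided. Two-sided is used below because it reproduces the plan's 60; one-sided 0.05 would give 48.

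**Formula.** Pooled-variance comparison of two proportions, without continuity correction:

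power = Φ[(|p1 − p2| − z × SE0) / SE1], with SE0 = √[p̄(1 − p̄)(1/n1 + 1/n2)] and SE1 = √[p1(1 − p1)/n1 + p2(1 − p2)/n2].

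**Numbers for 15 vs 45.**
- p̄ = (15 × 0.52 + 45 × 0.15)/60 = 0.2425
- SE0 = √[0.2425 × 0.7575 × (1/15 + 1/45)] = 0.1278
- SE1 = √[0.52 × 0.48/15 + 0.15 × 0.85/45] = 0.1395

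**Step 1: the plan's own figure.** At two-sided 0.05, z = 1.960. (0.37 − 1.960 × 0.1278)/0.1395 = 0.857, so power is 80.4%. The smallest sample for 80% at a 1:3 split is 15 + 45 = 60, so the plan's sample size is reproduced.

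**Step 2: the stated analysis level as a fixed cut-off.** At two-sided 0.025, z = 2.241. (0.37 − 2.241 × 0.1278)/0.1395 = 0.599, so power is 72.5%. Enumerating all possible tables with the uncorrected chi-square test gives 72.2%.

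**Step 3: all 70 evaluable, level 0.025.** The same formula at 1:3 (17.5 vs 52.5) gives 79.1%. Exact enumeration with whole women gives 80.8% (17 vs 53) and 81.4% (18 vs 52).

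**Step 4: Benjamini-Hochberg as named.** The cut-off at rank k is 0.10 × k/32. The stated 0.025 is the rank-8 step (0.10 × 8/32). Power for 15 vs 45 by the formula above:

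| Rank k | Cut-off | Power |
|---|---|---|
| 1 | 0.003125 | 47.8% |
| 8 | 0.025 | 72.5% |
| 16 | 0.05 | 80.4% |
| 32 | 0.10 | 87.4% |

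The power of the primary test therefore depends on how many of the 32 comparisons are rejected, which cannot be known in advance.

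**The case against.** **The primary comparison is named.** The Sample size calculation belongs to the statistical analysis section and specifies PIS against raised LVEDP, with both groups and both rates. The sentence before the aim in the Introduction already points there ("the absence of pulmonary interstitial syndrome (PIS) may exclude raised LVEDP"), and the accuracy analysis addresses "pre- and post-test probabilities of PIS to predict elevated LVEDP". This stands. A reader might infer that the plan leaves the primary comparison open, or intends to choose among cardiac definitions later. The documents do not support that: the Introduction is less specific than the sizing text, not in conflict with it. Nor does leaving raised LVEDP out of the first outcome list demote it. That list only governs which prevalences receive confidence intervals, and raised LVEDP receives the same treatment in the next sentence.

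**72.5% is not what Benjamini-Hochberg yields.** This also stands. The figure applies only if p < 0.025 is used as a fixed cut-off, which is how the plan states it. Under the ranked procedure the power may fall on either side of 80%. The plan's 80% is then no better supported.

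**The shortfall may vanish with 70 women.** In part. A reader might infer that 80% power at 0.025 needs 72 evaluable women and so cannot be reached with 70. That rests on the normal approximation; exact power with 70 evaluable is slightly above 80%. But the extra 10 women are there to cover unusable images, and the plan's stated requirement is 60.

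**Including the primary outcome in the correction is a deliberate choice.** It may be, and the sponsor may keep it. The power statement then has to follow from it.

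One reconciliation fails. Two-sided 0.05 and one-sided 0.025 give the same test, but the plan attributes 0.025 to its 32 comparisons, not to a one-sided test.

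**Conclusion.** The mismatch is real and limited. The sample size arithmetic is correct for a two-sided 0.05 test. At the level stated in the analysis text, used as a fixed cut-off, 60 evaluable women give about 72% power (72.5% by approximation, 72.2% exact), a loss of about 8 percentage points from 80.4%. If all 70 are evaluable, power is about 79% to 81%. Under ranked Benjamini-Hochberg it runs from about 48% at the strictest step to 87% at the most lenient, so it cannot be stated in advance.

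These figures assume the plan's own rates of 52% and 15%, its 1:3 split by LVEDP, a two-sided test and no continuity correction. The difference in wording of the primary aim is a matter of precision and should be tidied at the same time. It is not evidence of an undefined or movable primary outcome.

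**What to change.** In F) Statistical analysis, state which significance level applies to the primary test of PIS in women with raised versus normal LVEDP. Two options are coherent:

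- **(a)** Test it alone at two-sided 0.05, apply the Benjamini-Hochberg correction to the secondary comparisons only, and recount the 32. The sample size and the 80% power are unchanged. The cost is a 5% instead of a 2.5% chance of a false positive on that one test.
- **(b)** Keep it under p < 0.025, say that this is a fixed cut-off, and restate the power in the Sample size calculation as about 72% for 60 evaluable women. The cost is a lower declared power.

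In the Introduction, replace the general reference to cardiac dysfunction in the primary aim with raised LVEDP, so that it matches the sizing text.

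All of these are wording changes. Neither option alters procedures or recruitment.

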## II. Methods

In this prospective cohort study, preeclamptic women presenting with new onset tonic-clonic, focal, or multifocal seizures in the absence of other causative conditions such as epilepsy, cerebral arterial ischemia and infarction or intracranial hemorrhage arising from non-obstetric pathology, or drug use, will be enrolled. Preeclampsia will be defined according to the recommendations of the American College of Obstetricians and Gynecologists (Table 1). Early onset disease will be defined as diagnosis before 34 weeks of gestation, and late onset disease as after 34 weeks. Given the high prevalence of the disease and the presence of established detailed management protocols, data collection will be performed in the Maternity Centre at Groote Schuur Hospital at the University of Cape Town, Cape Town, South Africa.

Table 1: ACOG diagnostic criteria for preeclampsia

Blood Pressure	
 
• > 140 mmHg systolic <math>\pm</math> 90 mmHg diastolic after 20 weeks gestation
 
• (Severe: > 160 mmHg systolic <math>\pm</math> 110 mmHg diastolic)
 

&	
Proteinuria	
 
• 300 mg in 24h or
 
• Prot./Creat. ratio > 0.3 or
 
• > 1+ dipstick
 

OR in absence of proteinuria, new onset hypertension AND presence of $\geq 1$ severity feature:	
Thrombocytopenia	
 
• <math><100 \times 10^9 / L</math>
 

Renal insufficiency	
 
• serum creatinine <math>>1.1 \text{ mg/dl}</math> or <math>\times 2</math>
 

Impaired liver function	
 
• 2 x LFTs
 

Pulmonary edema	
Cerebral or visual symptoms	

### **A) Patient screening, enrolment, inclusion, non-inclusion and consent**

On a daily basis, the obstetrics consultant and/or senior registrar in charge will inform the anaesthesia member of the research team should a patient be eligible for the study and her clinical condition allow recruitment and conduction of the ultrasound protocol.

The patient will be approached after completion of normal obstetric treatment protocols, and asked for permission to study their medical file for research purposes. After screening

for inclusion and non-inclusion criteria, the patient will be enrolled and written consent obtained. For details of the consent process, please see III. Ethics Considerations, pages 16-17.

**B) Inclusion / Non-inclusion criteria**

Inclusion criteria are diagnosis of preeclampsia following ACOG definition (Table 1) with new onset of tonic-clonic seizures. Non-inclusion criteria are chronic pulmonary disease, collagen disorders, HIV infection, chronic renal or hepatic disease, urinary tract infection, sepsis, and body mass index (BMI)  $> 50 \text{ kg/m}^2$ , history of seizure disorder, intracranial hemorrhage, or history of benign or malignant intracranial neoplasia.

**C) Exclusion criteria**

Following consent and inclusion in the study, women either withdrawing consent, or not giving retrospective consent, will be excluded.

**D) Time point of ultrasound examination**

Maternal ultrasound examinations will be performed after normal obstetric treatment protocols have been completed, i.e., the conduction of the study will contribute no delay in routine or emergency patient management. Ultrasound examination will be repeated after 72-96 hours, subject to the same conditions.

**E) Ultrasound procedures**

An ultrasound examination (approximately 35-40 minutes in duration) will be performed, at which time a venous blood sample will be taken. In addition to venepuncture for measurement of BNP, an additional 2 x 5 ml samples (in vacutainer serum separation collection tubes) will be taken for storage (-80°C) and subsequent batch serum measurement of sFlt-1, PIGF and Kisspeptin as surrogate biomarkers for placental dysfunction. The ultrasound examination will consist of evaluation of lung- and cardiac ultrasound, as well as optic nerve sheath diameter.

**Ea) Cardiac Ultrasound:**

### *Eaa) 2D echocardiography*

The cardiac ultrasound examination will be performed using a GE Vivid Q® ultrasound machine equipped with a 3.5-MHz transducer. Images will be acquired at rest in the left lateral decubitus position from standard parasternal and apical views. Digital loops of 3 cardiac cycles with associated electrocardiogram information will be stored on the hard disk of the ultrasound machine and transferred to a GE EchoPac® work-station for offline analysis. Analysis will be performed according to existing guidelines. Ventricular wall and chamber dimensions will be measured in the parasternal long axis view. Left atrial volume (LAV) and left ventricular volume in diastole (LVEDV) will be calculated from apical views. Right atrial area, right ventricular basal and mid cavity diameter and right ventricular longitudinal diameter will be measured from apical views. Proximal and distal right ventricular outflow tract (prox. and dist. RVOT) will be measured in parasternal short axis views. Tricuspid annular plane systolic excursion (TAPSE) will be measured from apical M-Mode images. Right ventricular fractional area change will be calculated from apical views. Doppler images will be used to measure early and late mitral and tricuspid valve inflow velocities (E and A, RV E and RV A), mitral and tricuspid inflow deceleration time (DT, RV DT), isovolumetric relaxation time (IVRT), systolic and diastolic flow in the pulmonary veins, duration of the late mitral valve inflow (A dur), duration of the flow in the pulmonary vein during atrial contraction (AR dur) and acceleration time of the flow through the pulmonary valve (PV acc. time). Tissue Doppler images will be used to measure systolic (S'), early diastolic (E') and late diastolic (A') tissue velocities at the septal and lateral mitral valve and at the right ventricular free wall. Left ventricular mass will be calculated using the Devereux formula  $0.8(1.04[(LVEDD + IVSd + PWd)^3 - LVEDD^3]) + 0.6$ , where LVEDD is left ventricular end diastolic diameter, IVSd is thickness of the interventricular septum in diastole and PWd is posterior wall thickness in diastole. Relative wall thickness will be calculated using the formula  $(2*PWd)/LVEDD$ . Total vascular resistance (TVR) will be calculated using the formula  $80*MAP/(CO/1000)$ , where MAP is mean arterial pressure and CO cardiac output. Diastolic dysfunction will be classified according to the guidelines of the American Society of Echocardiography and European Society of Cardiovascular Imaging, applying the age and gender adapted values from the 2016 Guidelines.

*Eab) Speckle tracking echocardiography*

The myocardium will be traced manually and EchoPac® software used to identify the area of interest, by delimiting the endocardium and epicardium. The operator will readjust this area before the software will calculate deformation. LV and RV global longitudinal strain and strain rate will be calculated from apical views, with negative values indicating fiber shortening. LV rotation and de-rotation will be calculated from apical and basal parasternal short axis views, with negative values indicating rotation in the clockwise direction. LV twist is the difference between the apical and the basal rotation, LV torsion is LV twist divided by left ventricular length in diastole. If >1 segment is rejected, subjects will be excluded from statistical analysis.

Eb) Lung Ultrasound

Lung ultrasound will be performed with the patient in the supine position. A phased-array transducer will be used for lung ultrasound, and will be used for the assessment of B-lines, which arise from the pleural line and extend to the bottom of the screen, and move with the sliding lung (Figure 1). We will quantify the B-line burden in lung regions using the validated eight-region method, as previously described: Two anterior and two lateral regions in each hemithorax will be evaluated. If 3 or more B-lines (any size and spaced apart by any distance) are present in a particular region, that region is considered positive. Two or more positive regions per side define a “B-line pattern.”

Ec) Ultrasound of optic nerve sheath (ONS)

Measurement of optic nerve sheath diameter will be performed applying the coronal technique with a linear transducer placed in a vertical (cephalad-caudal) orientation at the lateral canthus and aimed nasally and posteriorly until a circular optic nerve is seen at its largest diameter. Measurements will be taken in a superior-inferior direction to minimize artifact if the image is taken at a slightly oblique angle (Figure 2). The patient will be positioned supine (with or without left uterine displacement, depending on clinical circumstances), with a 30 degree head elevation. After the point of entry of the optic nerve into the globe has been identified, the image will be frozen. Optic nerve sheath diameter

will be measured 3 mm behind the globe in a perpendicular axis to the nerve (Figure 3). Two measurements will be taken per eye, and the mean of the 4 values will represent the optic nerve sheath diameter.

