4 In view of recent work showing that in South Africa teenage mothers are at highest risk of eclampsia (Nathan et al, Journal of Global Health 2018:8: 020401), we request that minors (patients under the age of 18 years) may also be recruited for these noninvasive ultrasound scans. In these circumstances, parental approval will be requested, together with assent by the patient. The same initial waiver is respectfully requested for a patient requiring mechanical ventilation, as in 3, above. “Delayed consent” would then involve requesting parental approval and the assent of the patient after recovery. Should it be impossible to make contact with the parents, the research group will contact the HREC for a decision in the individual case.

4 In the unusual event of a diagnosis of intracerebral haemorrhage or stroke, the patient will be excluded from the study. In the rare event of the demise of a patient for any reason other than intracerebral haemorrhage or stroke, the researchers request that the data be included and analysed, after discussion with the HREC, for the reasons below.

The justifications for the above consent process and data inclusion are the following: Exclusion of patients without the capacity for consent, including minors, would lead to a biased sample, and data which is not generalisable to the majority of women with eclampsia. The generation of biased and poorly generalisable data would not address the research question and would thus dishonour the contributions of the other included patients, and would be wasteful research in a resource-limited environment.

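### Does the speckle-tracking image-quality rule take women out of the primary lung–heart comparison?

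*Combined protocol and SAP*

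**What the plan says.** The rule is the last sentence of Methods, section Eab (Speckle tracking echocardiography). It applies when more than one "segment is rejected, subjects will be excluded from statistical analysis", and the analysis meant is not named.

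The surrounding text bears on its reach:

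- The Introduction places strain among the secondary aims: "performance of a comprehensive cardiac ultrasound assessment including a strain analysis".
- Section C (Exclusion criteria) deals with consent only: "women either withdrawing consent, or not giving retrospective consent, will be excluded". Ethics section B (Informed Consent) adds a diagnosis of intracerebral haemorrhage or stroke, in which case "the patient will be excluded from the study".
- Section Eaa (2D echocardiography) covers the Doppler and tissue Doppler measures and the diastolic grading: "Diastolic dysfunction will be classified according to the guidelines of the American Society of Echocardiography". PIS is read from B-lines in section Eb (Lung Ultrasound).
- Section F (Statistical analysis) says that associations "between cardiac and pulmonary ultrasound abnormalities, will be explored". It defines no analysis set and does not mention strain.
- The sample size paragraph states the primary aim as to "examine the association between PIS on lung ultrasound and raised LVEDP on cardiac ultrasound". It explains the margin over 60 as follows: "To allow for the possibility of poor image acquisition during positive pressure ventilation, 70 patients will be recruited".

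**The concern.** The sentence excludes subjects, not strain values, and its last two words match the title of section F, which holds the lung–heart comparison. No other section limits it. A literal reader could therefore drop women whose lung scan and LVEDP assessment are both readable, because of a secondary measurement.

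Three things would be at stake. Two analysts could report different primary denominators from the same data. The women lost would be those with poor images, who are not a random subset; the plan itself expects poor images in ventilated patients. And power would fall, because the 10-woman margin was set for another cause of loss.

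**Working it through.** **1. Which reading the text supports**

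| Place | What it shows |
|---|---|
| Eab, position of the rule | It follows directly on the definitions of strain, rotation, twist and torsion. A rejected segment belongs to this technique; the lung method counts regions, and the Doppler measures have their own subsection. |
| C, and Ethics B | Exclusions from the study are listed in these places, and image quality is not among them. |
| F | The named ultrasound outcomes are PIS, diastolic dysfunction, increased optic nerve sheath diameter, systolic dysfunction and raised LVEDP. Strain is not one of them. |
| Sample size | The step from 60 to 70 covers image problems under positive pressure ventilation only. A strain rule meant to thin the primary set would be an obvious further loss, and none is allowed for. |
| Sample size, earlier data | PIS is 23/95 and raised LVEDP 20/80. Separate denominators fit measure-by-measure analysis, although the reason for the difference is not given. |

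The wording taken alone favours the wide reading. Everything around it favours the strain-only reading.

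**2. Reproducing the planned size**

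Inputs from the sample size paragraph: PIS in 52% of women with raised LVEDP and 15% of women with normal LVEDP, 15 against 45 women, 80% power, significance level 0.05. Two-sided testing is assumed, since it reproduces the stated number.

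- Pooled rate: (0.52 + 3 × 0.15)/4 = 0.2425.
- Smaller group: [1.96 × √(0.2425 × 0.7575 × 4/3) + 0.8416 × √(0.52 × 0.48 + 0.15 × 0.85/3)]² / 0.37² = (0.970 + 0.455)² / 0.1369 = 14.8, rounded up to 15.
- Total: 15 + 45 = 60, as the plan states.

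**3. Power if the rule did reach the primary test**

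At 15 and 45:

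- Standard error under no difference: √(0.2425 × 0.7575 × (1/15 + 1/45)) = 0.1278.
- Standard error under the alternative: √(0.2496/15 + 0.1275/45) = 0.1395.
- Power = Φ[(0.37 − 1.96 × 0.1278)/0.1395] = Φ(0.857) = 80.4%.

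With the 1:3 split kept, both standard errors scale with √(60/N), so power is about Φ(2.651 × √(N/60) − 1.795). The rejection rates below are assumptions.

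| Strain rejection (assumed) | From 70, no other loss | From 60, margin already used |
|---|---|---|
| 0% | 70: 85.7% | 60: 80.4% |
| 5% | 66.5: 84.1% | 57: 78.5% |
| 10% | 63: 82.2% | 54: 76.4% |
| 20% | 56: 77.8% | 48: 71.8% |

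Power reaches 80% at N = 59.3, a loss of (70 − 59.3)/70 = 15.3%. In whole patients, losing 10 leaves 60 (80.4%) and losing 11 leaves 59 (79.8%).

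The right-hand column is the worst case: all 10 spare women are lost for other reasons, and the strain failures then fall on different women. Poor acoustic windows could well cause both kinds of failure, and any overlap brings the figures back towards 80.4%.

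**4. Power under the strain-only reading**

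The rule removes nobody from the primary comparison: 80.4% with 60 evaluable women, 85.7% with 70.

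**The case for a change.** The strongest case for a change is that placement suggests scope without stating it. The sentence names subjects and statistical analysis without a qualifier. A rule that could alter the primary denominator is best settled before results are seen, or the choice might be made afterwards. A few words would settle it. The plan also argues, in its consent section, against an unrepresentative sample, and needless losses tied to image quality would cut against that.

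Part of this stands. The scope is not written down, and no passage can be cited that closes the question. What does not stand is the step from silence to harm. Nothing in the documents shows an intention to apply the rule beyond strain, and several features point the other way. No rejection rate is given, and no direction or size of bias in the PIS–LVEDP association is shown.

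One caution applies to the other side too. The documents do not spell out the criteria for raised LVEDP, and the Introduction words the primary aim more broadly, as cardiac dysfunction on echocardiography. That the primary test makes no use of strain is therefore a well-supported inference, not a stated fact.

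A new sentence defining the primary set is also not quite free. It would have to fit with the separate haemorrhage and stroke exclusion, or it would open a new question while closing this one.

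**Conclusion.** The concern does not call for a change. There is a real but minor looseness of wording, of the kind analysts fill sensibly. A quality rule at the end of a measurement subsection governs that measurement, and each table carries its own n. On that reading the effect on the primary comparison is zero.

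On the literal reading, all 70 recruited women would have to yield fewer than 60 usable records, that is, more than 10 lost from all causes together, before power fell below 80%. With assumed strain-rejection rates of 5% to 20%, power would run from 84.1% to 77.8% if nothing else were lost, and from 78.5% to 71.8% if the whole margin had already gone. These figures rest on the plan's 52% and 15%, the 1:3 split, a two-sided 0.05 test with pooled variance, and rejection rates that the documents do not supply. The conclusion would need another look only if strain images were in fact used to decide who has raised LVEDP, and nothing in the documents says so.
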